4.11 Safety Evaluation

All safety summaries and analyses will be based upon the Safety Population as defined in Section 4.4 of this document.

All summaries will be provided by treatment group.

Placebo across treatment group will be pooled.

4.11.1 Adverse Events

A treatment-emergent adverse event (TEAE) is defined as an AE that begins or that worsens in severity after at least one dose of the study drug has been administered.

Any AEs with incomplete start and end dates/times will be treated as per

Table 6-2.

Adverse events will be coded using the MedDRA Version 23.1 or higher.

A table of the number (percentage) of subjects and number of adverse events with treatment emergent adverse events (TEAEs) will be presented and summarized by SOC, PT and treatment group. If more than one event with the same preferred term occurred for the same subject, then the subject will be counted only once for that preferred term.

A table of the number (percentage) of subjects and number of adverse events with TEAEs will be presented and summarized by SOC, PT, relationship, and treatment group. If more than one event with the same preferred term occurred for the same subject, then the subject will be counted only once with the highest relationship for that preferred term.

A table of the number (percentage) of subjects and number of adverse events with TEAEs, summarized by SOC, PT, severity, and treatment group will be presented. If more than one event occurred with the same preferred term for the same subject, then the subject will be counted only once with the maximum severity level of that preferred term.

Adverse event summaries will be ordered in terms of decreasing frequency for SOC, and PT within SOC, in the test treatment group, and then similarly by decreasing frequency in the reference treatment group, and then alphabetically for SOC, and PT within SOC.

For each subject and each adverse event, the worst severity recorded will be attributed and used in the by-severity summaries. Similarly, the worst causality (most related to treatment) will be attributed and used in the by-causality summaries. If severity or causality is missing, a conservative approach for AE assessment (taking into account the worst case) will be followed.

A by-subject listing of all adverse events (including non-treatment-emergent events) will be provided. This listing will be presented by treatment group and will include: subject identifier, adverse event (SOC, PT, and verbatim term), date of onset, date of resolution, duration, severity, seriousness, action taken, outcome and causality.

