2.2 Secondary Objectives

The secondary objectives of this study are:

- To assess the effects of therapeutic and supratherapeutic setmelanotide concentrations on Heart rate (HR), PR interval, QRS interval, T-wave morphology, and cardiac safety in healthy subjects.
- To evaluate assay sensitivity and the effect of a positive control, a single 400 mg oral dose of moxifloxacin, on the QT/QTcF interval in healthy subjects.

- To assess the pharmacokinetics (PK) of setmelanotide following administration of therapeutic and supratherapeutic doses of subcutaneous (SC) setmelanotide in healthy subjects.
- To evaluate the safety and tolerability of therapeutic and supratherapeutic doses of SC setmelanotide in healthy subjects.

- [REDACTED]

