3.1 Overall Study Design and Plan

This is a double-blind, randomized, placebo- and positive-controlled, parallel group, 3-arm study to assess the potential for therapeutic and supratherapeutic concentrations of SC setmelanotide administered as IMCIVREE to affect the QTcF interval compared with placebo. Approximately 72 healthy subjects aged 18 to 50 years of age, inclusive, are planned to be enrolled in the United States. Subjects will be enrolled into 1 of 3 groups as follows:

- Group 1: SC setmelanotide; oral placebo on Days 10 and 16
- Group 2: SC placebo; oral moxifloxacin on Day 10 and oral placebo on Day 16
- Group 3: SC placebo; oral placebo on Day 10 and oral moxifloxacin on Day 16.

The study design is presented in [Figure 3-1](#).

Figure 3-1 Study Design Schematic

Upon providing informed consent, subjects will enter a 28-day Screening period, during which they will be assessed for eligibility and complete all screening procedures as described in the Schedule of Assessments (SoA) ([Table 6-1](#)).

Following the Screening period, eligible subjects will check-in to the Clinical Research Unit (CRU) on the morning of Day -2. Subjects will be randomized 1:1:1 into Group 1, 2, or 3 and will be fasted overnight (for at least 10 hours). On the morning of Day -1 following a standard breakfast, subjects will undergo 24-hour continuous ECG Holter monitoring beginning 30 minutes after the meal (at the time of anticipated dosing on Days 10 and 16). Baseline assessments ([Table 6-1](#)) will occur on Day -1.

On the morning of Day 1, subjects will receive SC setmelanotide 2 mg (Group 1) or SC placebo (Groups 2 and 3) in a double-blinded fashion.

From Days 2 to 16 following a standardized breakfast, subjects will continue receiving SC setmelanotide (3 mg QD from Days 8 to 10; 5 mg QD from Days 11 to 13; 7 mg QD from Days 14 to 16) or SC placebo according to their assigned group. On Days 10 and 16, oral placebo or oral moxifloxacin 400 mg will be administered with the SC dose according to the assigned dose group. Continuous Holter ECGs and PK sampling will be conducted on Days 10 and 16 pre-dose and for up to 24 hours post-dose according to the SoA ([Table 6-1](#)). All treatments administered in the CRU will be double-blinded and will be given at the same time every day (approximately 30 minutes after the start of breakfast).

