4.2.1 Treatment

The following treatments will be administered as follows:

- SC setmelanotide: SC injection: 2 mg × 7 days followed by 3, 5, and 7 mg × 3 days per dose level
- SC placebo (matched to active setmelanotide): SC placebo injection × 16 days
- Oral moxifloxacin: single oral dose of 400 mg moxifloxacin
- Oral placebo (matched to oral moxifloxacin): single oral placebo dose

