^d Supine blood pressure, supine heart rate, pulse rate, and tympanic (ear) body temperature. Heart rate and blood pressure will be measured using the same arm for each reading after the subject has been resting in the supine position for at least 5 minutes. For timepoints at which vital signs, PK blood samples, and/or ECGs are all to be collected, ECGs should be collected first followed by vital signs then PK samples, with the timing of the PK sample to occur at the nominal time.

^e Serum pregnancy test will be performed at Screening. Urine pregnancy test will be performed on all other designated days.

^f On the evening before continuous ECG sampling, subjects will undergo a 10-hour overnight fast.

^g Breakfast is to be administered at approximately 7:00 AM every day in the CRU (30 minutes pre-dose). Lunch, dinner, and a snack will be administered at approximately 12:00 PM (after 4-hour assessments), 6:00 PM (after 10-hour assessments), and 9:00 PM, respectively.

^h **Group 1** will receive SC setmelanotide QD (approximately 7:30 AM) at a dose of 2 mg from Days 1 to 7; 3 mg from Days 8 to 10; 5 mg from Days 11 to 13; and 7 mg from Days 14 to 16.

Groups 2 and 3 will receive SC placebo QD (approximately 7:30 AM) from Days 1 through 16.

All doses will be double-blinded.

ⁱ **Group 1** will receive oral placebo with their SC setmelanotide dose on Days 10 and 16.

Group 2 will receive oral moxifloxacin 400 mg on Day 10 and oral placebo on Day 16.

Group 3 will receive oral placebo on Day 10 and oral moxifloxacin 400 mg on Day 16.

All doses will be double-blinded. On Days 10 and 16, subjects should receive SC setmelanotide/placebo first. Oral moxifloxacin/placebo should then be administered within 2 minutes of the SC dose.

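### No planned adverse event table separates therapeutic from supratherapeutic setmelanotide doses, although a secondary objective names both

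*SAP*

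**What the plan says.** SAP 2.2 lists the secondary objective: "To evaluate the safety and tolerability of therapeutic and supratherapeutic doses of SC setmelanotide in healthy subjects". Protocol 4.2 has the same objective.

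There is one active group, which SAP 3.1 gives as "Group 1: SC setmelanotide; oral placebo on Days 10 and 16". Its subjects move through every dose step. The schedule in SAP 6.1 starts them at "2 mg from Days 1 to 7", and SAP 4.2.1 describes the remainder as "followed by 3, 5, and 7 mg", three days at each level. SAP 4.2.1 lists this whole sequence as a single treatment.

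For safety, SAP 4.11 states "All summaries will be provided by treatment group" and "Placebo across treatment group will be pooled". SAP 4.11.1 plans three TEAE tables: overall ("summarized by SOC, PT and treatment group"), by relationship, and by severity. If a preferred term recurs in a subject, "then the subject will be counted only once for that preferred term"; the relationship and severity tables keep the highest relationship and the maximum severity. Protocol 11.3.4 also summarizes adverse events by treatment group.

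Two listings bear on the point. The adverse event listing in SAP 4.11.1 includes the onset date but not the dose at onset. The exposure listing in SAP 4.9.1 gives each dose with its date and time.

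**The concern.** The objective distinguishes dose ranges and the adverse event tables do not. Events in the first week on 2 mg and events on 7 mg fall in the same column, and the once-per-term rule can merge them into one subject. A mild event on 2 mg followed by a severe recurrence on 7 mg appears in the severity table as one severe subject with no dose attached. The tables also give a number of events, which keeps both occurrences but does not locate either by dose.

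This matters for the terms most likely to recur. The protocol synopsis says the titration is there to reduce gastrointestinal effects seen when treatment starts. Such terms may be counted early, and a return at a higher dose would then add nothing to the subject count. Protocol 5.6 also allows doses to be delayed or decreased and escalation to be postponed. Subjects who never reach 7 mg stay in the Group 1 denominator, so incidence at 7 mg cannot be read from the tables.

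**Working it through.** **1. Is treatment group meant to include dose level?** No. For Holter data, SAP 4.10.3.1 names treatment group, day, dose level and time point as separate strata. Dose level is thus distinct from treatment group in the SAP's own usage, and SAP 4.11 and 4.11.1 name only the group.

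**2. Dosing days by step** (SAP 3.1 and 6.1). The plan's stated duration reproduces: 7 + 3 + 3 + 3 = 16 days.

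| Step | Days | Share of 16 | Subject-days, n = 24 | Subject-days, n = 20 |
|---|---|---|---|---|
| 2 mg | 7 | 43.75% | 168 | 140 |
| 3 mg | 3 | 18.75% | 72 | 60 |
| 5 mg | 3 | 18.75% | 72 | 60 |
| 7 mg | 3 | 18.75% | 72 | 60 |
| Total | 16 | 100% | 384 | 320 |

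Here n = 24 is 72/3 at planned enrolment and n = 20 is the planned completers. Both assume no dropout and no dose adjustment. At or below 3 mg: (7 + 3)/16 = 62.5%. Above 3 mg: 6/16 = 37.5%.

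**3. The table column is longer than the dosing period.** SAP 4.11.1 defines a TEAE as starting or worsening after at least one dose, and Protocol 10.2.5 records adverse events through the Follow-up visit, planned for Day 23 ± 2. With follow-up on Day 23 there are 16 dosing days and 7 later days. Assuming the same event rate every day:
- share at or below 3 mg: 10/23 = 43% (10/25 = 40% to 10/21 = 48% for follow-up on Day 25 to Day 21);
- share at 7 mg: 3/23 = 13%.

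**4. Dilution, as an illustration.** The rates are assumed. Suppose the daily rate on 5 and 7 mg days is twice the rate on all other days.
- Dosing days only: (10 × 1 + 6 × 2)/16 = 22/16 = 1.375, a rise of 37.5%.
- Full column to Day 23: (10 + 12 + 7)/23 = 29/23 = 1.26, a rise of 26%.

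A doubled rate would therefore raise the column total by about a quarter, and nothing in the table would show at which dose.

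**5. Placebo comparator.** Group 2 takes moxifloxacin on Day 10 and Group 3 on Day 16. With 24 subjects per group, pooled placebo for Days 11 to 15 is 48 × 5 = 240 subject-days. The moxifloxacin-free part is Group 3 alone, 24 × 5 = 120, or half.

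**The case against.** The strongest reply is that nothing is lost. Onset dates and dated doses are both listed, so dose at onset can be worked out for every event in about 24 subjects. That is correct. A reader might infer that the safety objective cannot be answered; the documents do not support this. The group tables also still describe safety over the whole titration against placebo.

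A reader might also infer that the trial's only supratherapeutic safety information is merged. That is wrong as well. Holter descriptives are split by day and dose level (SAP 4.10.3.1), and Holter outliers by day (SAP 4.10.3.2.1). Laboratory results are summarized by time point, and vital signs and C-SSRS by time of collection. Only the adverse event tables merge the doses.

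A third tempting reading is that 62.5% of the events in the column arise at therapeutic doses. That figure is a share of dosing days; step 3 gives the share of the column.

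It can also be said that safety is descriptive throughout, that the dose order is fixed and that the later steps last only three days, so no table can attribute events to dose. This stands and limits what the addition can show. It does not explain why the dose split is planned for Holter data and not for adverse events. Finally, a redacted section or a table shell outside the documents might contain a by-dose display. The visible text contains none.

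**Conclusion.** The point holds for adverse event tabulation and no further. None of the planned TEAE tables distinguishes dose steps, and the once-per-term and maximum-severity rules can merge events across them. The by-dose part of the objective is left to hand-matching two listings.

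The day counts assume the planned schedule without adjustment or dropout. The 43% and 26% figures also assume follow-up on Day 23 and the stated daily rates, which are not in the documents. The primary QTc analysis is unaffected. This is an inexpensive improvement that lets the trial report on its own objective.

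**What to change.** - **Derive actual dose at onset** as the last SC dose received before the event, and add it to the adverse event listing. The scheduled day is not enough, because Protocol 5.6 permits departures from the schedule.
- **Add descriptive Group 1 TEAE tables** (overall, relationship, severity) with columns for 2, 3, 5 and 7 mg and a separate post-treatment column for events after the last dosing day. Keep 5 and 7 mg apart: Protocol 5.4 labels 3 mg as maximum therapeutic and 7 mg as supratherapeutic and does not class 5 mg.
- **Count each subject once per preferred term within each step**, and show subjects and subject-days at risk, since the steps differ in length and not every subject may reach each one.
- **Show placebo for the matching scheduled days**, with Group 2 time after its Day 10 moxifloxacin dose and Group 3 time after its Day 16 dose shown separately. State that the moxifloxacin-free comparator for Days 11 to 15 is Group 3 only, and that the matching is approximate where escalation was postponed.
- **State in the SAP that the display is descriptive**, because dose is confounded with time on drug.

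The cost is one derived variable and a few more tables with small denominators. No new data or change in trial conduct is needed, and the SAP introduction allows for an updated version.

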4.11.2 Deaths, Serious Adverse Events, and Other Significant Adverse Events

Listings of SAEs, deaths and other significant adverse events will be provided along with SAEs and AEs leading to withdrawal from treatment or study.

4.11.3 Clinical Laboratory Evaluation

Blood samples for clinical laboratory tests are to be drawn as per shown in [Table 6-1](#).

Specific tests are described below:

- **Hematology:** complete blood count with platelet count and standard indices will be obtained.

- **Chemistry:** sodium, potassium, chloride, carbon dioxide (CO₂), albumin, total protein, glucose, blood urea nitrogen (BUN), creatinine, uric acid, aspartate aminotransferase (AST), alanine aminotransferase (ALT), gamma-glutamyltranspeptidase (GGT), creatine phosphokinase (CPK), alkaline phosphatase, total bilirubin, direct bilirubin, lactate dehydrogenase (LDH), calcium and phosphorus.
- **Coagulation Profile:** prothrombin time (PT) or international normalized ratio (INR), and partial thromboplastin time (PTT), also referred to as activated partial thromboplastin time (aPTT).
- **Urinalysis:** pH, glucose, protein, ketones, bilirubin, blood, urobilinogen, specific gravity, nitrite, and leukocytes by dipstick analysis or machine urinalysis. Urine microscopic examination will be performed if positive findings on dipsticks warrant further examination.

Clinical laboratory test results of hematology, chemistry, coagulation profile and urinalysis will be provided by treatment group.

All TLFs will display only the standard international (SI) units after conversion by means of standard conversion factors.

Quantitative clinical laboratory variables, ie, hematology, chemistry, coagulation profile, and urinalysis will be summarized using descriptive statistics (n, mean, SD, minimum, maximum and median) by treatment group and time-point. Additionally, a within-participant change will be calculated as the post-baseline measurement minus the baseline measurement and summarized in the same way.

Baseline definition will be defined in section [4.2.4](#).

Any quantitative laboratory parameters that are given as '<xx' or '>xx' in the database will be imputed with the absolute value of the number without the sign (e.g., <2.2 will be imputed as 2.2) for the calculation of the changes from baseline and for the descriptive statistics. In the listings, no imputations will be performed, and all data will be displayed as recorded in the database.

Each laboratory result will be classified as low (L), normal (N), or high (H) at each time point according to the laboratory supplied reference ranges. For hematology and biochemistry, shift tables will be presented showing the number and percentage of subjects with shifts from baseline to each postdose time point. Tabulations will be presented by treatment group.

Measurements obtained at Screening and End of Study (EOS) will not be included in the shift tables.

Measurements obtained prior to dosing in each period will be included in the tabulations for the treatment received in that specific treatment period.

Frequency tabulations of qualitative clinical laboratory variables (urinalysis) will be presented by treatment group and time-point.

All laboratory data will be displayed in listings.

Laboratory abnormalities that are considered clinically significant (CS) are recorded in the database as AEs. Therefore, no tabulation of laboratory values meeting any CS criteria (except liver chemistry) will be presented as all relevant information will be presented in the AE summaries.

Results of pregnancy tests (females only), urine drugs screen tests will be listed only.

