- Frequency and severity of AEs (assessed separately for relation to SC setmelanotide and/or oral moxifloxacin), clinical laboratory evaluations, safety ECGs, C-SSRS score, vital signs, and physical examinations

Statistical methods:***Cardiodynamic Holter ECG Assessment:***

The primary analysis will be based on C-QTc modeling of the relationship between plasma concentrations of setmelanotide (or placebo) and Δ QTcF (using Day -1 time-matched Holter ECGs as baseline) with the intent to exclude an effect of $\Delta\Delta$ QTcF >10 msec at clinically relevant plasma levels, using the concepts presented in the “Scientific White Paper on C-QTc modeling” (Garnett 2018b, Garnett 2018a). After development of the C-QTc model and assessment of model performance through nonparametric bootstrapping, the $\Delta\Delta$ QTcF associated with the Cmax of therapeutic and supratherapeutic doses will be computed using bias-corrected 90% CI. An increase in QTc of 10 msec or greater can be ruled out if the upper 90% CI is <10 msec.

The change from baseline (Δ) and placebo-corrected change from baseline ($\Delta\Delta$) QTcF, HR, PR, and QRS will be summarized by nominal time and treatment using descriptive statistics. An analysis of categorical outliers will be performed for changes in QTcF, HR, PR, and QRS, and T-wave morphology, and U-wave presence and results will be summarized.

Assay sensitivity will be evaluated by C-QTc analysis of the effect on $\Delta\Delta$ QTcF of moxifloxacin using a similar model as for the primary analysis. Assay sensitivity will be deemed as met if the predicted QT effect (i.e., the lower bound of the 2-sided 90% CI of $\Delta\Delta$ QTcF) is above 5 msec at the observed geometric mean Cmax of 400 mg oral moxifloxacin.

Pharmacokinetics:

Setmelanotide and moxifloxacin concentration data will be summarized by nominal time point and treatment using descriptive statistics. PK parameters for setmelanotide and moxifloxacin (as listed in the PK endpoints section) will be calculated using noncompartmental methods (NCA) and summarized by treatment.

Safety:

All AEs will be listed and TEAEs will be summarized using descriptive methodology (setmelanotide and moxifloxacin AEs reported separately). Each AE will be coded using the Medical Dictionary for Regulatory Activities (MedDRA). Observed values for clinical laboratory test data, 12-lead safety ECGs, C-SSRS score, vital signs measurements, and physical examination findings will be listed.

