2. SCHEDULE OF ASSESSMENTS

The Schedule of Assessments (SoA) is presented in [Table 1](#).

Table 1: Schedule of Assessments

Study Period	Screening		Check-In	Baseline	Treatment										Follow-up	Treatment Discontinuation
Study Day Assessment	-28 to -2		-2	-1	1	2-6	7	8	9	10	11-14	15	16	17	23 ± 2	7 ± 4 days after last SC dose
Informed consent	X															
Inclusion/exclusion review	X		X													
Medical history review	X															
Physical exam ^a	X			X											X	X
Comprehensive skin exam ^b	X															
Fitzpatrick classification scale	X															
Height and weight ^c	X			X											X	X
Vital signs ^d	X			X											X	X
Pregnancy test ^e	X			X												X
FSH test	X			X												
Urine drug screen	X			X												
CRU confinement			X	X	X	X	X	X	X	X	X	X	X			
CRU discharge														X		
Fasting ^f			X					X				X				

Study Period	Screening	Check-In	Baseline	Treatment											Follow-up	Treatment Discontinuation
Study Day Assessment	-28 to -2	-2	-1	1	2-6	7	8	9	10	11-14	15	16	17	23 ± 2	7 ± 4 days after last SC dose	
Meal administration ^g			X				X	X	X	X	X	X	X			
Setmelanotide administration ^h				X	X	X	X	X	X	X	X	X	X			
Moxifloxacin administration ⁱ									X				X			
PK sampling ^j									X			X				
Continuous 12-lead ECGs (Holter monitor) ^{k,l}			X							X			X			
Safety 12-lead ECGs ^{l,m}	X		X			X							X	X	X	
Clinical labs ⁿ	X		X			X							X	X	X	
Adverse events	X			Continuous											X	
Concomitant medication review	X			Continuous											X	
C-SSRS ^o	X		X										X		X	
		■								■						

Study Period	Screening		Check-In	Baseline	Treatment												Follow-up	Treatment Discontinuation
Study Day Assessment	-28 to -2		-2	-1	1	2-6	7	8	9	10	11-14	15	16	17		23 ± 2	7 ± 4 days after last SC dose	

CRU = Clinical Research Unit; C-SSRS = Columbia Suicide Severity Rating Scale; ECG = electrocardiogram; FSH = follicle stimulating hormone; INR = international normalized ratio; PK = pharmacokinetic; PT = prothrombin time; PTT (or aPTT) = partial thromboplastin time.

^a A full physical exam will be conducted at Screening. A brief physical exam will be conducted at each check-in, baseline, study discharge, and follow-up.

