^j Blood samples for quantification of setmelanotide and moxifloxacin concentrations will be collected at pre-dose and 0.5, 1, 1.5, 2, 2.5, 3, 4, 5, 6, 7, 8, 9, 10, 12, 16, and 24 hours post-dose on Days 10 and 16. The PK samples collected at 0.5 hours post-dose will have a sampling window of \pm 2 minutes, samples collected from 1 hour though 2.5 hours post-dose will have a sampling window of \pm 5 minutes, samples collected from 3 hours through 10 hours post-dose will have a sampling window of \pm 10 minutes, and samples collected from 12 through 24 hours postdose will have a sampling window of \pm 20 minutes; however, collection of samples outside of the window will not be considered protocol deviations. The timing of all PK samples should be recorded to the nearest minute. For timepoints at which vital signs, PK blood samples, and/or ECGs are all to be collected, ECGs should be collected first followed by vital signs then PK samples, with the timing of the PK sample to occur at the nominal time.

^k Holter ECGs will be extracted at Day -1 and on Days 10 and 16 at the following timepoints: pre-dose and 0.5, 1, 1.5, 2, 2.5, 3, 4, 5, 6, 7, 8, 9, 10, 12, 16, and 24 hours post-dose. The Day -1 extractions will begin at 7:30 AM (the time of anticipated dosing on Days 10 and 16).

^l For ECG collection, subjects will rest in the supine position for at least 10 minutes before and 5 minutes after each timepoint. For timepoints at which vital, PK blood samples, and/or ECGs are all to be collected, ECGs should be collected first followed by vital signs then PK samples, with the timing of the PK sample to occur at the nominal time.

^m Safety ECGs will be collected at the Screening visit, CRU baseline (Day-1), final CRU discharge, and the Follow-up visit.

ⁿ Safety clinical laboratory tests will include: hematology with platelet count and standard indices, chemistry panel (includes sodium, potassium, chloride, CO₂, albumin, total protein, glucose, BUN, creatinine, uric acid, AST, ALT, GGT, CPK, alkaline phosphatase, total bilirubin, direct bilirubin, LDH, calcium, phosphorus, magnesium), and urinalysis with microscopic analysis if positive findings on dipsticks warrant further examination. Safety laboratories will also include a coagulation profile (PT or INR, and PTT also referred to as aPTT).

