11.3.4. Safety Analysis

AEs will be coded by using the most current version of Medical Dictionary for Regulatory Activities (MedDRA) and summarized by system organ class, preferred term, and treatment group for the number and percent of AEs reported, the number of subjects reporting each AE, and the number of subjects with any AE.

A by-subject AE data listing including onset and resolution dates, verbatim term, preferred term, treatment, severity, relationship to treatment, action taken, and outcome will be provided.

Safety data, including 12-lead safety ECGs, C-SSRS, clinical laboratory evaluations, vital signs, and concomitant medication monitoring will be summarized by time of collection and by treatment group. In addition, change from baseline to any post-dose values will be summarized for safety ECGs, C-SSRS, clinical laboratory results, and vital signs. Frequency of subjects with abnormal safety laboratory results will be tabulated by treatment.

No formal statistical analysis of safety data is planned.

[REDACTED]

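### SAP 4.11.3 does not deliver the protocol's count of subjects with abnormal laboratory results: coagulation has no abnormality count, and the shift tables leave out an undefined EOS visit

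*SAP*

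**What the plan says.** Protocol 11.3.4 states: "Frequency of subjects with abnormal safety laboratory results will be tabulated by treatment". It limits this neither by panel nor by visit. The protocol's schedule footnote on clinical laboratory tests counts hematology, chemistry, urinalysis and a coagulation profile as safety laboratory tests.

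SAP 4.11.3 begins broadly: "Each laboratory result will be classified as low (L), normal (N), or high (H) at each time point". The tables that follow are narrower:

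- Shift tables are planned for hematology and biochemistry only. They are described as showing "shifts from baseline to each postdose time point".
- The next paragraph restricts them: "Measurements obtained at Screening and End of Study (EOS) will not be included in the shift tables".
- Urinalysis has separate frequency tables by treatment group and time point.
- Clinically significant abnormalities are not tabulated as laboratory data, apart from an unspecified exception for liver chemistry, because they are recorded as adverse events.
- All laboratory data are listed.

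SAP 4.14, on changes to the planned analysis, has the entry Not Applicable.

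**The concern.** The SAP classifies every laboratory result as low, normal or high, but does not turn that classification into the count that the protocol names. One panel has no count at all. For two others, the table is said to cover every time point after dosing and then loses one of them, with no reason given.

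The omitted visit is also hard to identify. SAP 4.2.3 defines the end of the study only as a trial-level date, the last visit of the last subject, and no column of the schedule is called EOS. A programmer would have to guess.

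The wording may be template text carried over. A neighbouring sentence speaks of dosing in each period, which does not fit a parallel-group study. The same exclusion recurs in SAP 4.11.5, where no shift table is described. That is an inference, but it makes a deliberate choice less likely.

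At stake is the completeness of the descriptive safety tables. A subject frequency by treatment shows an imbalance between arms in a way that listings and means do not. Routing abnormalities through adverse events depends on the investigator's judgment of significance; the protocol's table does not.

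**Working it through.** The plan gives no figure to reproduce, so the check sets the provisions side by side.

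**Step 1: panels.** Each safety laboratory panel against what SAP 4.11.3 provides:

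| Panel | Descriptive statistics by time point | Table counting abnormal results | EOS excluded from that table |
|---|---|---|---|
| Hematology | yes | shift table by visit | yes |
| Chemistry | yes | shift table by visit | yes |
| Urinalysis | yes | frequency table by visit | not stated |
| Coagulation | yes | none | does not apply |

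Of four panels, two have shift tables, one has frequency tables and one has no abnormality count.

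**Step 2: visits.** In the protocol's schedule, the "Clinical labs" row has entries at Screening, Day -1, Day 7, Day 17, Follow-up (Day 23 ± 2) and Treatment Discontinuation. A subject who completes therefore has three laboratory visits after the first dose: Day 7, Day 17 and Follow-up. Protocol 5.5 ties a subject's completion to Follow-up, so that is the most natural meaning of EOS. On that reading the shift tables use 3 − 1 = 2 of the three visits. Day 7 falls in the 2 mg stage of the titration, so for a completer in Group 1, Day 17 would be the only shift-table visit after the 3 mg and 7 mg stages.

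**Step 3: what reaches no count table.** SAP 4.11.3 says clinically significant laboratory abnormalities are recorded as adverse events. Protocol 10.2.5 records adverse events through Follow-up, so these are counted there. What remains is values outside the reference range but not judged clinically significant:

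- coagulation results at any visit; and
- hematology or chemistry results first out of range at EOS.

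**Step 4: by visit or by subject.** Even for hematology and chemistry, the SAP specifies no table of subjects with at least one abnormal value. It cannot be recovered from by-visit counts: with two visits, the number of subjects with at least one abnormal value lies anywhere between the larger of the two counts and their sum, depending on overlap.

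**Step 5: declaration.** The SAP's table set is narrower than Protocol 11.3.4, and SAP 4.14 does not say so.

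**The case against.** The strongest reply is that little is lost.

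- Clinically significant abnormalities at the last visit, coagulation included, enter the adverse event summaries.
- Urinalysis has its own frequency tables, and the EOS sentence is written for shift tables only.
- Descriptive statistics and changes from baseline, with minimum and maximum, cover all four panels with no EOS exclusion. Every value is listed.
- The protocol synopsis promises no abnormality table: "Observed values for clinical laboratory test data, 12-lead safety ECGs, C-SSRS score, vital signs measurements, and physical examination findings will be listed".
- Safety is to be described only, without hypothesis tests.

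All of this is correct, and it limits the point to non-significant out-of-range values. It does not supply the count that Protocol 11.3.4 names, and a shorter synopsis does not cancel the body of the protocol.

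A second reply is that the protocol's sentence does not ask for a count over any post-dose visit. That is also right. The any-post-dose wording belongs to a different commitment: "change from baseline to any post-dose values will be summarized for safety ECGs, C-SSRS, clinical laboratory results, and vital signs". By-visit shift tables could therefore be defended as meeting part of the sentence for hematology and chemistry. They still leave out coagulation and EOS, although the sentence excludes neither.

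A reader might go further and infer that subjects who stop early lose their discontinuation result from the tables. The documents do not support that. The exclusion names Screening and EOS; the SAP's abbreviation list gives EOS and early termination (ET) separate entries; and nothing equates EOS with the Treatment Discontinuation visit. The SAP simply does not say how that visit is handled.

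**Conclusion.** The concern holds as a narrow, undeclared gap between Protocol 11.3.4 and SAP 4.11.3. Coagulation has no abnormality count, no per-subject count is specified for the quantitative panels, and EOS is removed from shift tables that the SAP itself says cover every post-dose time point.

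The size in visits is one of three for a completer, and it rests on reading EOS as Follow-up, which is an inference. The number of subjects affected cannot be estimated: the documents give no rate of out-of-range values and no timing of dropout, so any percentage would only restate an assumption.

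It would be wrong to conclude that abnormalities first seen at the last visit go uncounted in general, or that the shift tables are the only tables of abnormal results. The priority is low, a desirable improvement. The primary QTc conclusion does not depend on it.

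**What to change.** In SAP 4.11.3:

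1. Delete the EOS exclusion from the shift-table sentence.
2. State that Follow-up and Treatment Discontinuation are post-dose time points for laboratory data.
3. Add one table by treatment giving, per analyte, the number and percentage of subjects with at least one low or high value after the first dose, for hematology, chemistry and coagulation. Keep by-visit rows beside it, because Follow-up is about a week off drug and should be readable separately.

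If the sponsor prefers the narrower scope, define EOS as a named visit, then declare and justify the difference from Protocol 11.3.4 in SAP 4.14.

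The cost is a few lines of SAP text and one table. The data are already collected and already classified as low, normal or high.
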